In addition, the main effect of each plasma inflammatory factor on DFS and OS will be examined. For the main effect, plasma levels will be divided into quintiles for the analysis. Baseline characteristics of patients will be compared according to quintiles of the biomarker using Wilcoxon signed rank tests for continuous variables and chi-squared tests for categorical variables. For primary analyses of survival, patients who recurred or died within three months of plasma collection will be excluded to minimize any bias due to occult cancer recurrence or preclinical illness. In sensitivity analyses, the possibility of reverse causation will be assessed by allowing different lag times between plasma assessment and cancer recurrence or death. The log-rank test and Kaplan-Meier curves will be used to compare DFS OS by quintile of plasma level. Cox proportional hazards models will be used to control for multiple confounders. The two-tailed *P* value for the linear trend test across categories will be calculated using the plasma level as a continuous variable, consistent with prior studies.

The primary efficacy variable for analyses will be disease-free survival (DFS). Secondary efficacy endpoint will be overall survival.

For the main effect of plasma 25(OH)D (**Objective 1.3**), plasma 25(OH)D levels will be divided into quintiles for the analysis. Baseline characteristics of patients will be compared according to quintiles of the biomarker using Wilcoxon signed rank tests for continuous variables and chi-squared tests for categorical variables. For primary analyses of survival, patients who recurred or died within three months of plasma collection will be excluded to minimize any bias in the 25(OH)D level due to occult cancer recurrence or preclinical illness. In sensitivity analyses, the possibility of reverse causation will be assessed by allowing different lag times between 25(OH)D assessment and cancer recurrence or death. The log-rank test and Kaplan-Meier curves will be used to compare DFS OS by quintile of 25(OH)D level. Cox proportional hazards models will be used to control for multiple confounders. The two-tailed *P* value for the linear trend test across categories will be calculated using the 25(OH)D level as a continuous variable, consistent

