Objective 1.5 is to identify the features from whole transcriptome analysis which are associated with DFS. As outliers in both the time-to-event observations and gene expressions may be encountered, the length of follow-up varies among patients, and multiple markers are considered, methods which are robust, are able to incorporate the censoring mechanism, and allow for incorporation of multiplicity adjustments will be employed. The association between the time-to-event endpoint and each of the features will be quantified using the non-parametric rank-covariance measure.¹⁴⁵ This method is a non-parametric counterpart to Cox regression where the time-to-event variable is regressed on the ranks of the expression. The family-wise error rate (FWER) adjusted exact permutation P-values will be calculated using B=10,000 permutation replicates. Features will be considered significant at the 0.05 FWER adjusted level.

We are interested in the association between each feature and DFS. Kendall's tau will be used to quantify these pairwise associations. This quantity is uniquely determined by the copula generating the joint (bivariate) distribution between each feature and DFS and as such is invariant to marginal distributions. It will be assumed that the marginal effects are continuous so as to ensure uniqueness of the generating copula.

An additional objective of gene expression assessment (**Objective 1.6**) is to identify those features for which there is expression by celecoxib interactions with respect to DFS. These analyses will be carried within the framework of two-way multiplicative Cox models.

The analyses outlined for the primary endpoint, will be carried out for OS and AE as well. For the adverse event endpoints, the two-sample Wilcoxon test will be employed to investigate the association between each feature and outcome.¹⁴⁶ For this endpoint, conditional inference tree and random forests methods for binary outcomes will be used.

The classification models for DFS, OS and adverse events in the previous models were based on molecular data. As additional exploratory analyses, the inclusion of clinical or demographic co-variables will be considered.

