Functional annotation of discovered signature will be performed by Gene Set Enrichment Analysis (GSEA)¹⁶ using the Molecular Signature Database (MSigDB, [REDACTED]). Survival data analyses will be performed using the log-rank test and multivariate Cox regression. All analyses were performed using GenePattern¹⁸ [REDACTED] or the R statistical package [REDACTED].

For the analysis of CIMP (**Objective 1.7**), the primary efficacy variable for analyses will be disease-free survival (DFS). Secondary efficacy endpoints include recurrence-free survival (RFS) and overall survival (OS).

Baseline characteristics of patients will be compared according to CIMP-high vs. CIMP-low/0 using Wilcoxon signed rank tests for continuous variables and chi-squared tests for categorical variables. The log-rank test and Kaplan-Meier curves will be used to compare DFS and OS by CIMP-high vs. CIMP-low/0. Cox proportional hazards models will be used to control for multiple confounders including MSI, BRAF, and LINE-1 status. In secondary analyses, we will examine how the relationship between CIMP status and patient outcome is modified by relevant covariates such as age, ECOG performance status and treatment assignment, MSI, BRAF, and LINE-1 status among others. Tests for statistical interaction will be performed by entering into the model the cross-product term of the CIMP status (binary variable) with the covariate as a continuous or binary variable. The main independent effect of BRAF and LINE-1 status on DFS will also be assessed using the aforementioned COX models.

For the analysis of immune response (**Objective 1.8**), the primary efficacy variable for analyses will be disease-free survival (DFS). Secondary efficacy endpoints include recurrence-free survival (RFS) and overall survival (OS). Interactions with celecoxib randomized will also be determined.

The prognostic association of TIPC-based CRC subtypes and DFS will be determined, with stratification by celecoxib randomization. In exploratory analyses statistical interaction of TIPC subtype and F. nucleatum level will be assessed.

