4.4 Data Analyses

The primary efficacy variable for analyses will be disease-free survival (DFS). Secondary efficacy endpoints include recurrence-free survival (RFS) and overall survival.

Exposure definitions: For all dietary exposures (**Objective 1.1**) including dietary insulin index, intakes will be categorized into energy-adjusted quintiles, consistent with our previous studies. In addition, physical activity will be categorized into categories of MET-hours as previously defined in prior work. Body mass index (kg/m²; Aim 2) will be divided into World Health Organization categories of underweight, normal weight, overweight and obesity.

For the main effect of plasma analytes (**Objective 1.2**; C-peptide, IGFBP-1, IGF-1, IGFBP-3, and adiponectin), plasma levels will be divided into quintiles for the analysis. Baseline characteristics of patients will be compared according to quintiles of the biomarker using Wilcoxon signed rank tests for continuous variables and chi-squared tests for categorical variables. For primary analyses of survival, patients who recurred or died within three months of plasma collection will be excluded to minimize any bias in the due to occult cancer recurrence or preclinical illness. In sensitivity analyses, the possibility of reverse causation will also be assessed by allowing different lag times between plasma assessment and cancer recurrence or death. The log-rank test and Kaplan-Meier curves will be used to compare DFS and OS by quintile of plasma level. Cox proportional hazards models will be used to control for multiple confounders. The two-tailed P value for the linear trend test across categories will be calculated using the plasma level as a continuous variable, consistent with prior studies. In secondary analyses, we will examine how the relationship between a specific plasma analyte level and patient outcome is modified by relevant covariates such as ECOG performance status, treatment assignment, physical activity and body mass index, among others. Tests for statistical interaction will be performed by entering into the model the cross-product term of the plasma level as a continuous variable with the covariate as a continuous or binary variable.

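### Baseline comparisons between independent marker groups name the Wilcoxon signed-rank test, a paired or one-sample test that cannot be validly run there

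*Combined protocol and SAP*

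**What the plan says.** The same test is named in four places.

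- **Appendix II, section 5.0, plasma inflammatory factors (main effect).** The groups are quintiles: "For the main effect, plasma levels will be divided into quintiles for the analysis". The comparison is then specified: "Baseline characteristics of patients will be compared according to quintiles of the biomarker", "using Wilcoxon signed rank tests for continuous variables".
- **Appendix II, section 5.0, Objective 1.3 (25(OH)D).** The same specification is repeated, again across quintiles.
- **Appendix II, section 5.0, Objective 1.7 (CIMP).** Baseline characteristics are "compared according to CIMP-high vs. CIMP-low/0 using Wilcoxon signed rank tests for continuous variables".
- **Appendix IV, section 4.4, Objective 1.2** (C-peptide, IGFBP-1, IGF-1, IGFBP-3, adiponectin). Baseline characteristics are "compared according to quintiles of the biomarker using Wilcoxon signed rank tests for continuous variables".

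Elsewhere the plan names the independent-groups version. For gene expression against adverse events, Appendix II section 5.0 says "the two-sample Wilcoxon test will be employed to investigate the association between each feature and outcome". Appendix III section 5.4.5 also names a two-sample Wilcoxon test, for copy-number markers against adverse events. Nothing in the documents corrects or qualifies the signed-rank wording.

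**The concern.** The signed-rank test works on within-pair differences, or on one sample against a fixed value. Neither structure exists here. A patient's single baseline level places that patient in one quintile, and a tumor is either CIMP-high or CIMP-low/0. The groups therefore hold different patients, and no matching is described.

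At stake is whether the planned p-values for continuous baseline variables can be produced at all. An analyst following the text literally cannot run the quintile comparisons. For CIMP the analyst could run the test only by inventing a pairing, and then only if the two groups happened to be the same size.

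**Working it through.** The plan gives no figure to reproduce, because the point concerns the choice of test. The check sets the test's requirements against the stated groups and then illustrates the consequence by simulation.

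**1. What the test needs.** For pairs (x_i, y_i), form d_i = x_i − y_i, rank |d_i|, and sum the ranks of the positive differences. Without a rule linking x_i to y_i, d_i is undefined.

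**2. Five quintiles (three of the four places).** The statistic is built from one set of differences, so it has no five-group form. Kruskal-Wallis does: H = [12 / (N(N+1))] × Σ(R_j² / n_j) − 3(N+1), where R_j is the rank sum and n_j the size of group j, on 5 − 1 = 4 degrees of freedom (without ties).

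**3. Two CIMP groups (one place).** The documents give no CIMP prevalence, and nothing makes the groups equal. If the sizes differ, patients cannot be paired one to one. With 300 against 1,200 patients (assumed sizes), the routine returned an error.

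**4. Two equal groups, paired arbitrarily.** Inputs:
- From Appendix II, Table 3: 1,500 patients (60% of samples), hence 1,500 / 5 = 300 per quintile.
- Assumed, not in the documents: a baseline variable distributed Normal with mean 61 and SD 11; 1,000 replicates with no true difference.

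| Test | Null rejection rate at 0.05 |
|---|---|
| Kruskal-Wallis, five groups | 0.048 |
| Rank-sum, two groups | 0.056 |
| Signed-rank, two groups in arbitrary pairs | 0.059 |

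The Monte Carlo standard error at 0.05 is √(0.05 × 0.95 / 1,000) = 0.007, so all three rates are compatible with the nominal level. Arbitrary pairing does not grossly inflate type I error. What it loses is reproducibility. One fixed dataset was drawn with 300 patients per group and true means of 61 and 63 (a 2-unit shift, assumed). Over 2,000 re-pairings of that dataset:

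| Quantity | p-value |
|---|---|
| Signed-rank, smallest | 0.038 |
| Signed-rank, 2.5th percentile | 0.105 |
| Signed-rank, median | 0.225 |
| Signed-rank, 97.5th percentile | 0.409 |
| Signed-rank, largest | 0.555 |
| Rank-sum (does not depend on patient order) | 0.274 |

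The same patients can thus fall on either side of 0.05 depending only on how the file is sorted.

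**5. Does replacing signed-rank with rank-sum settle it?** For CIMP, yes. For quintiles, no: rank-sum compares two groups, and five quintiles give 5 × 4 / 2 = 10 pairwise comparisons with no stated rule for choosing among or combining them.

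**The case against.** The strongest reply is that this is a misnomer. The plan clearly intends a between-group comparison, it pairs the test with a chi-squared test that suits independent groups, and it names the two-sample Wilcoxon correctly elsewhere. Software would refuse the five-group analysis, so an analyst would substitute something sensible and a wrong result would be unlikely to reach a report. Much of this stands. The intent is plain, and rank-sum is probably what was meant. It does not close the point, because rank-sum is not a five-group test, so for three of the four places the reader still cannot tell which analysis is planned.

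A reader might also infer more than the documents support:

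- **That these tables choose the Cox covariates.** No section says so. Appendix II refers to adjustment for confounders without tying their selection to baseline tests, and for CIMP it names MSI, BRAF and LINE-1 status in advance.
- **That each group would be tested against a median of zero.** Such a test would always reject for a positive variable such as age (100% of simulated replicates), but the plan proposes comparison between groups, not a one-sample test.
- **That all the groups are unequal in size.** Quintiles are near equal by construction; unequal size is an issue only for CIMP.
- **That any resulting p-values would be meaningless.** Under arbitrary pairing of equal groups the error rate stays near nominal. Arbitrary and not reproducible is the accurate description.

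**Conclusion.** The point holds as an error in the stated analysis: in four places across two appendices, a paired or one-sample test is named for independent groups. It cannot be run across quintiles. For two groups it either cannot be computed or gives a p-value that depends on an arbitrary pairing. This conclusion rests on the groups as the plan defines them and needs no numerical assumption; the simulated p-values are illustrations under the assumptions stated.

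The consequence is minor. Only descriptive baseline comparisons in optional companion studies are affected. Associations of the markers with DFS and OS are assessed by log-rank tests and Cox models, and the trial's primary analysis is the stratified log-rank test in section 13.1. None of these changes.

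**What to change.** Amend the test for continuous baseline variables in four places:

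- **Appendix II, section 5.0, inflammatory factors and 25(OH)D (both), and Appendix IV, section 4.4:** name the Kruskal-Wallis test, or another k-sample rank test, across quintiles.
- **Appendix II, section 5.0, Objective 1.7:** name the two-sample Wilcoxon rank-sum test for CIMP-high versus CIMP-low/0.

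The chi-squared tests for categorical variables can stay. The cost is wording only: no new data, no change to sample size or error rates, and no effect on any DFS or OS analysis.

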6.0 STATISTICAL CONSIDERATIONS

The three clinical endpoints are adverse events (e.g., neuropathy), disease-free survival (DFS) and survival (OS). The exact definitions for these outcomes will be equivalent to those specified in the treatment protocol (CALGB/SWOG C80702). The treatment by biomarker (or genotype) interactions will be tested for the celecoxib hypothesis. If an interaction is present, relevant hypotheses will also be tested in the treatment groups of patients receiving and not receiving celecoxib. If no interaction is present, the treatment groups will be combined (celecoxib + no celecoxib) for analysis. Power estimates for specified differences in interaction are given in Table 3. Table 4 contains power estimates for DFS comparisons of biomarker and genotype within treatment group (celecoxib; no celecoxib) by marker prevalence, detectable hazard ratio and the percent of samples available. Table 5 provides power estimates for testing the prognostic value of a marker when no treatment by marker interaction is present. Table 6 illustrates detectable differences in DFS for biomarkers quantified in quartiles. Table 7 illustrates the difference detectable with the specified power for a biomarker quantified in quartiles versus a dichotomous marker; for example, Vitamin D levels measured by plasma 25(OH)D versus K-ras mutational status. Tables 8 and 9 describe the power achieved to detect the illustrated difference in Grade 3+ toxicity rates versus a biomarker quantified in quartiles. Examples are Grade 3+ neutropenia and diarrhea versus body mass index.

Table 3. Approximate power to detect the specified hazard ratio for treatment (no celecoxib; celecoxib) by biomarker interactions with 60% (n=1,500) and 80% (n=2,000) of samples obtained (2-sided $\alpha=0.1$) assuming exponential survival, a dichotomous biomarker, equal sample sizes per group, and an overall event rate of 0.31 (775/2500).

n (events)	Hazard Ratio-Interaction	Power
	1.5	
1500 (465)		0.34,0.58,0.71
2000 (620)		0.47,0.71,0.81
	1.6	
1500 (465)		0.48,0.71,0.81
2000 (620)		0.63,0.83,0.90
	1.7	
1500 (465)		0.60,0.81,0.88
2000 (620)		0.76,0.91,0.95

Moderate to large interaction hazard ratios are detectable with adequate power.

Table 4. Power estimates for DFS comparisons of a dichotomous biomarker or genotype within treatment groups (e.g., patients receiving celecoxib) by marker prevalence, detectable hazard ratio and the percent of samples available (log rank test, 2-sided $\alpha=0.01, 0.05, 0.10$). Exponential survival, equal numbers of samples per treatment arm, and an overall event rate of 0.31 (775/2500) are assumed.

	Detectable Hazard Ratio	1.4	1.5	1.6
Marker/Genotype Prevalence	n (number of events)			
0.5				
	750 (233)	0.49,0.72,0.82	0.69,0.87,0.92	0.84,0.94,0.97
	1000 (310)	0.65,0.84,0.90	0.83,0.94,0.97	0.94,0.98,0.99
0.2				
	750 (233)	0.30,0.53,0.65	0.46,0.69,0.79	0.61,0.81,0.88
	1000 (310)	0.41,0.65,0.76	0.61,0.81,0.88	0.76,0.91,0.95
0.1				
	750 (233)	0.15,0.33,0.45	0.23,0.45,0.58	0.33,0.57,0.69
	1000 (310)	0.21,0.42,0.55	0.33,0.57,0.69	0.46,0.69,0.79

Adequate power is achieved to detect moderate to large hazard ratios for dichotomous biomarkers or genotypes with prevalence close to 50%. The power estimates at 50% prevalence are approximately correct for biomarkers or genotypes with prevalence $\geq 30\%$ and $\leq 70\%$. For biomarkers or genotypes with prevalence near 20% and, in particular, 10%, larger differences are detectable with adequate power.

Table 5. Power estimates for DFS comparisons of a dichotomous biomarker or genotype by marker prevalence for all patients, detectable hazard ratio, and the percent of samples available (log rank test, 2-sided $\alpha=0.01, 0.05, 0.10$). Exponential survival and an overall event rate of 0.31 (775/2500) are assumed.

	Detectable Hazard Ratio	1.2	1.3	1.4	1.5
Marker/Genotype Prevalence	n (number of events)				
0.5					
	1500 (465)	0.27,0.50,0.62	0.59,0.80,0.88	0.85,0.95,0.97	0.96,0.99,0.99
	2000 (620)	0.37,0.62,0.73	0.75,0.90,0.94	0.94,0.98,0.99	0.99,0.99,0.99
0.2					
	1500 (465)	0.15,0.34,0.47	0.37,0.61,0.73	0.62,0.82,0.89	0.82,0.93,0.96
	2000 (620)	0.22,0.44,0.56	0.51,0.74,0.83	0.78,0.91,0.95	0.92,0.98,0.99
0.1					
	1500 (465)	0.08,0.21,0.32	0.18,0.39,0.52	0.034,0.58,0.70	0.51,0.74,0.83
	2000 (620)	0.11,0.27,0.38	0.26,0.49,0.62	0.47,0.71,0.80	0.67,0.85,0.91

Adequate power is achieved to detect moderate to large hazard ratios for dichotomous biomarkers or genotypes with prevalence close to 50%. The power estimates at 50% prevalence are approximately correct for biomarkers or genotypes with prevalence $\geq 30\%$ and $\leq 70\%$. For biomarkers or genotypes with prevalence near 20% and, in particular, 10%, larger differences are detectable with adequate power.

Table 6. Approximate DFS hazard ratios (maximum versus minimum hazard under “least favorable configuration”) detectable with 70%, 80%, and 90% power for comparisons of a continuous biomarker categorized by quartiles for all patients and the percent of samples available (2-sided $\alpha=0.01, 0.05, 0.10$). The chi-square non-centrality parameters (ncp) are 20.66, 16.74, 14.16, respectively, 70%, 80% and 90% power, with $\alpha=0.01$; 16.21, 12.73, 10.46, respectively, for $\alpha=0.05$; and 8.67, 10.77, and 14.02, respectively, for $\alpha=0.1$. Exponential survival and an overall event rate of 0.31 (775/2500) are assumed.

	Detectable Hazard Ratio (DFS)		
Power	0.7	0.8	0.9
n (number of events)			
1500 (465)	1.64,1.53,1.47	1.72,1.60,1.54	1.82,1.70,1.64
2000 (620)	1.54,1.45,1.40	1.60,1.50,1.45	1.68,1.58,1.53

With 60 and 80% of samples studied, adequate power is achieved to detect moderate to large hazard ratios for biomarkers categorized by quartiles.

Table 7. Difference in median DFS detectable for a continuous marker categorized by quartiles (Biomarker 1) versus a second dichotomous biomarker (Biomarker 2) with approximate powers of 0.44, 0.68, 0.78, respectively, for 2-sided $\alpha=0.01, 0.05, 0.10$, with 60% of patients submitting samples and approximate powers of 0.61, 0.81, 0.88, respectively, for $\alpha=0.01, 0.05, 0.10$, with 80% of patients submitting samples (logrank test). Exponential survival, equal sample sizes per group, and an overall event rate of 0.31 (775/2500) are assumed.

	Median DFS (years)			
Biomarker 1	Quartile(1)	Quartile(2)	Quartile(3)	Quartile(4)
Biomarker 2				
Absent	8.0	9.0	10.0	11.0
Present	9.0	8.0	7.0	6.0

Moderate to large interaction hazard ratios are detectable with adequate power.

Table 8. Power estimates to detect the difference illustrated in Table 9 for a continuous marker categorized by quartiles versus toxicity (< Grade 3+; \geq Grade 3+) for 60% (ncp=9.2) and 80% (ncp=12.3) of patients submitting samples (chi-square, 2-sided $\alpha=0.01, 0.05$).

	Significance Level	
n	$\alpha=0.01$	$\alpha=0.05$
1500 (60% of patients)	0.67	0.85
2000 (80% of patients)	0.82	0.93

Table 9. Difference in proportions of patients by a continuous marker categorized in quartiles versus toxicity (< Grade 3+; \geq Grade 3+) that is detectable with power given in Table 8. A Grade 3+ toxicity prevalence of 0.3 is assumed.

Biomarker	Quartile(1)	Quartile(2)	Quartile(3)	Quartile(4)	Total
Adverse Event					
< Grade 3+	0.1875	0.18	0.175	0.1625	0.7
\geq Grade 3+	0.0625	0.075	0.075	0.0875	0.3
Total	0.25	0.25	0.25	0.25	1.0

For gene expression analyses, we will assume that 775 events are expected in the clinical study. This corresponds to an event rate of 0.31. We will assume that 70% will provide consent and usable samples for these analyses. The corresponding sample size and number of events to be used for the power calculations are 1750 and 542 respectively. For these simulations, we will assume that the DFS distribution is mixture of exponentials, with rates $-\log(0.72)/3$ and $-\log(0.77)/3$ respectively, and that the censoring distribution is uniform. The parameters on the latter are chosen so as to set the expected event rate is 0.31. The power, at the two-sided 0.01 FWER Bonferroni adjusted level, is illustrated in Table 10 based on a Kendall tau coefficient of 0.11, 0.12 and 0.13 under the Gaussian, Frank and Gumbel copulas. Each illustration is based on 10,000 Monte Carlo simulations. As we have pointed out, we will sharpen these FWER bounds through permutation resampling for the analyses.

Table 10. Power illustration for the gene expression study at the two-sided 0.05 FWER level

tau	Copula	Power
0.11	Normal	0.79
0.12		0.91
0.13		0.97
0.11	Frank	0.82
0.12		0.92
0.13		0.98
0.11	Gumbel	0.54
0.12		0.71
0.13		0.84

A molecular classification model will be constructed using conditional inference trees with binary splits.³⁸ These trees will allow for direct incorporation of the censoring mechanism, which is important given that the length of follow-up varies among patients, as well as adjustment for multiplicity. The overall error rate will be adjusted at the 0.2 level using permutation resampling. The terminal nodes of these trees will be considered "risk" groups (classified by the trees). Kaplan-Meier estimates of the hazard profiles for these risk groups will be produced and presented graphically. We will also consider the random forests for survival data.³⁹⁻⁴¹ One of the key advantages of the two methods is that they implicitly incorporate interactions among the variables.

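### Table 4 of Appendix II gives the power of the within-arm marker test alone, but the written rule reaches that test only after an interaction is found, and the power of the two steps together is not stated

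*Combined protocol and SAP*

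**What the plan says.** Appendix II, section 6.0 sets a two-step rule for biomarkers and genotypes. The interaction of the marker with celecoxib assignment is tested. Then: "If an interaction is present, relevant hypotheses will also be tested in the treatment groups of patients receiving and not receiving celecoxib". And: "If no interaction is present, the treatment groups will be combined (celecoxib + no celecoxib) for analysis".

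The section assigns tables to these steps. Table 3 covers the interaction. For the next step, "Table 4 contains power estimates for DFS comparisons of biomarker and genotype within treatment group (celecoxib; no celecoxib) by marker prevalence". Table 5 covers the pooled analysis when there is no interaction. Table 4's caption describes a log-rank test at two-sided 0.01, 0.05 and 0.10 and adds: "Exponential survival, equal numbers of samples per treatment arm, and an overall event rate of 0.31 (775/2500) are assumed". For prevalence 0.5, HR 1.5 and 750 patients (233 events) it prints "0.69,0.87,0.92". The text beneath concludes: "Adequate power is achieved to detect moderate to large hazard ratios for dichotomous biomarkers or genotypes with prevalence close to 50" per cent.

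No significance level is given for declaring an interaction present. The only hint is the 0.1 in Table 3's caption. No table gives the probability of passing both steps.

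**The concern.** A within-arm finding needs two results under this rule: a significant interaction and then a significant marker effect in the arm. Its probability cannot exceed the power of the interaction test. For a marker with HR 1.5 in one arm and 1.0 in the other, the interaction HR is also 1.5. With 1,500 samples Table 3 gives that step 0.58 or 0.71 (the entries that correspond to alpha 0.05 and 0.10), while Table 4 gives 0.87 for the later step.

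Appendix II does contain a hypothesis of this kind. Section 2.1 predicts worse DFS and OS among celecoxib-treated patients whose normal tissue has low 15-PGDH, which is a marker comparison within one arm. Someone who takes Table 4 and its adequacy sentence as the power for such a finding would expect too much of the planned analysis.

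**Working it through.** **Inputs.** Events per arm D = 233 (60% of samples) or 310 (80%), prevalence p and marker HR are from Table 4. Total events E = 465 for the interaction are from Table 3. The current target of 696 DFS events is from section 13.1 of the main protocol. Two assumptions are not in the documents: the marker acts in one arm only, and the interaction is tested at 0.10 or at 0.05.

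**1. Reproduce Table 4.** One-stage power = Φ(√(D·p(1−p))·ln HR − z). For D = 233, p = 0.5, HR 1.5: √58.25 × 0.4055 = 3.095.
- alpha 0.01: Φ(3.095 − 2.576) = 0.698 (printed 0.69)
- alpha 0.05: Φ(3.095 − 1.960) = 0.872 (printed 0.87)
- alpha 0.10: Φ(3.095 − 1.645) = 0.926 (printed 0.92)

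All 54 entries reproduce within 0.010, so the table is single-stage.

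**2. Reproduce Table 3.** Interaction power = Φ(√(E/16)·ln HR − z). For E = 465, HR 1.5: √29.06 × 0.4055 = 2.186, giving 0.348, 0.589 and 0.706 at alpha 0.01, 0.05 and 0.10 (printed 0.34, 0.58, 0.71). The three columns therefore correspond to three levels, although the caption names only 0.1.

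**3. Joint power under the rule.** Let m = √(D·p(1−p))·ln HR in the arm where the marker acts, and zero in the other. The within-arm statistic has mean m. The interaction statistic has mean m/√2 and correlation 1/√2 with it. Joint power is the bivariate normal probability that both exceed their critical values in absolute size. In the example m = 3.095 and m/√2 = 2.188. The joint power is 0.68 with the interaction at 0.10 and 0.58 at 0.05. A simulation of 2,000,000 draws gave 0.680 and 0.576.

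**4. All alpha 0.05 cells**, HR 1.4 / 1.5 / 1.6:

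| Prevalence, events per arm | Printed | Rule, interaction at 0.10 | Rule, interaction at 0.05 |
|---|---|---|---|
| 0.5, 233 | 0.72 / 0.87 / 0.94 | 0.52 / 0.68 / 0.80 | 0.42 / 0.58 / 0.71 |
| 0.5, 310 | 0.84 / 0.94 / 0.98 | 0.64 / 0.80 / 0.90 | 0.54 / 0.71 / 0.83 |
| 0.2, 233 | 0.53 / 0.69 / 0.81 | 0.35 / 0.49 / 0.61 | 0.27 / 0.39 / 0.51 |
| 0.2, 310 | 0.65 / 0.81 / 0.91 | 0.45 / 0.61 / 0.74 | 0.36 / 0.50 / 0.64 |
| 0.1, 233 | 0.33 / 0.45 / 0.57 | 0.20 / 0.29 / 0.38 | 0.15 / 0.22 / 0.29 |
| 0.1, 310 | 0.42 / 0.57 / 0.69 | 0.26 / 0.38 / 0.49 | 0.20 / 0.29 / 0.39 |

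The shortfall against the printed value is 8.4 to 20.4 points with the interaction at 0.10 and 14.9 to 30.6 points at 0.05. Eight of the 18 printed cells reach 0.80. Under the rule three do (interaction at 0.10, to two decimals) or one does (0.05).

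**5. Sensitivity to the other arm** (prevalence 0.5, 233 events, HR 1.5 in one arm; printed 0.87).
- Other arm 1/1.5: 0.87 at either level. Across all 18 cells, equal and opposite effects cost at most about 1 point (0.10) or 3 points (0.05).
- Other arm 1/1.2: 0.85 or 0.82.
- Other arm 1.2: 0.33 or 0.22, although the pooled test then usually detects a marker effect.

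**6. Counting a pooled finding as detection.** With HR 1.5 against 1.0, the interaction step fails 29% or 41% of the time. Adding a significant pooled test at 0.05 after failure brings detection to 0.85 or 0.82. The pooled effect is √(1.5 × 1.0) = 1.22.

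**7. Current event target.** 696 × 0.6 / 2 = 208.8 events per arm. At prevalence 0.5, joint power at HR 1.4 / 1.5 / 1.6 is about 0.47 / 0.63 / 0.76 with the interaction at 0.10 and 0.37 / 0.53 / 0.66 at 0.05.

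**The case against.** The strongest defence is that Table 4 is right for what its caption says. Section 6.0 sets out power by step, and the weak first step stands in Table 3, directly before Table 4. At 50% prevalence the joint power is almost the interaction power (0.68 against 0.71), so a careful reader could get close to it unaided. Most celecoxib marker objectives in Appendix II (1.1, 1.2 and 1.6) concern effect modification, which is the interaction test itself. All of this stands. It limits the point to a missing joint power, a missing interaction level and an adequacy sentence that needs qualification.

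Three stronger readings are tempting, and the documents do not support them.
- A reader might infer that Table 4 is miscalculated. It is not: every entry reproduces. Its single event rate of 0.31 for both arms is a stated assumption, not an error.
- A reader might infer that a failed interaction leaves only a diluted pooled HR. Appendix II, section 5.0 also gives celecoxib-versus-placebo HRs with confidence intervals within each marker category, and Appendix III, section 5.1 does so by genotype; neither is conditional on an interaction. These answer a different question from marker-high versus marker-low within an arm, so they do not supply what Table 4 describes, but they remain.
- A reader might infer that a real one-arm marker would usually be missed altogether. Detection by either route is 0.85 or 0.82 in the example.

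**Conclusion.** The point holds in a limited form. Table 4 is the power of one step of a two-step rule, and the plan does not say so. For a marker acting in one arm only, the chance of a within-arm finding at alpha 0.05 is 8 to 20 points (interaction at 0.10) or 15 to 31 points (interaction at 0.05) below the printed value. The size rests on the one-arm scenario, on an interaction level the plan does not give, on equal events per arm and on the 775-event basis. It shrinks to a few points or less when effects oppose and grows when they point the same way. Severity is minor: only the correlative appendix is affected, and the trial's primary analysis is not.

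**What to change.** 1. In Appendix II, section 6.0, state the level at which an interaction is declared present. Label Table 4 as the power of the within-arm test alone. Add the joint power of the two steps on one stated event basis: 775 events with equal arms, using the values in step 4 of the working, or preferably the current 696, where step 7 gives the values for prevalence 0.5 and 60% yield and the other cells follow from the same formula. State the one-arm scenario beside the figures.
2. Qualify the adequacy sentence. At prevalence 0.5 and 60% yield, joint power at HR 1.6 is about 0.80 on 775 events and 0.76 on 696 with the interaction at 0.10, and 0.71 and 0.66 at 0.05.
3. Report the marker HR with its 95% CI within each arm for every marker, whatever the interaction p-value, as estimates and not tests.

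The cost is some wording, one added table and two further estimates per marker. The stated power becomes less favourable. No patients, samples or data are added.
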